2.3 Endpoints

The outcome measures will be assessed prior to the start of Outpatient Therapy, after 9 Outpatient PT visits , after 18 sessions and a 3 month follow up testing visit, which will be the endpoints of the study;

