10. **Stroke Impact Scale (SIS):** The SIS is a validated measure of the impact of stroke on overall physical and cognitive function. This 59-item patient-based questionnaire assesses eight domains of stroke recovery: strength, mobility, communication, emotion, memory and thinking, participation, activities of daily living/instrumental activities of daily living (ADL/IADL) and hand function. An additional question requires the patient to rate their stroke recovery on a scale from 0 to 100. This measure instructs subjects to answer the question based on the period of time two-four weeks prior to the questionnaire.
11. **Community Participation Indicators (CPI):** The CPI is an eighty-item self-report questionnaire that assesses the individual's satisfaction with their community participation.
12. **Visual Analog Scale or Numeric Pain Rating Scale:** The 0-10 rating scale for pain is used to gain a subjective report of the intensity of a person's pain. Zero represents "no pain" and ten represents "the most intense pain imaginable". A meaningful change would be plus or minus 3 points.
13. **Patient Health Questionnaire-9 (PHQ-9):** The PHQ-9 is a 9-item self-report screening assessment for depression. It is the depression module of the Diagnostic and Statistical Manual (4th edition). Each item is scored from 0-3; total scores may be 0-27, with higher scores representing increased severity of depression.
14. **Stroke Specific Quality of Life (SSQoL):** The SSQoL is a self-report questionnaire that is accepted as a reliable and valid way to assess health-related quality of life specific to stroke survivors. Subjects respond to 49 questions in 12 domains: mobility, energy, upper extremity function, work/productivity, mood, self-care, social roles, family roles, vision, language, thinking, and personality. Each item is rated on a 5-point Likert scale, with higher scores indicating better functioning. Domains scores (un-weighted average of item scores) and a summary score (un-weighted average of all 12 domain scores) are computed.

15. **TMS:** will assist researchers in generating recruitment curves which will help assess the corticospinal excitability of the ipsilateral and contralateral motor cortex to each lower limb muscle.

16.

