8.2 Sample Size and Accrual

A total enrollment of 80 subjects is estimated for this study. Each enrolled subject is randomly assigned to either one of the groups (SMA or IPT; 40 participants per group). A detailed description of study procedures and study endpoints are provided in section of 5.0

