8.3 Data Analyses Plans

The outcome measures for each subject (listed in Section 5.2) are recorded during 0th, 10th and 18th session of the training cycle and at 3 month follow up visit. Photographs and video without individual subject's faces will be recorded as this device is not commercially available yet and dissemination of accurate information will be assisted by showing how the device operates when donned and used by subjects. Outcome measures are compared with in the subject and across the subject pools for statistical significant differences using Multiple ANOVAs. All the statistics will be performed at 90% confidence level.

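### Nine listed outcomes that no objective names, including all seven self-reported measures, are significance-tested at the 90% level with no exploratory label or error control

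*Combined protocol and SAP*

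**What the plan says.** **Objectives.** Section 2.1 names one measure, the 10 meter walk test. Section 2.2 adds the 6MWT, BBS, FGA, 5xSST, a step counter and corticospinal drive.

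**Outcome list.** Section 5.2 lists 15 measures. Gait analysis (item 5), the FMA (item 7) and the self-reported measures (items 8-14: mFES, ABC, SIS, CPI, pain rating, PHQ-9, SSQoL) are named in no objective. Two of the self-reported measures have several parts. On the SIS: "This 59-item patient-based questionnaire assesses eight domains of stroke recovery", to which a 0-100 recovery rating is added. On the SSQoL: "Domains scores (un-weighted average of item scores) and a summary score (un-weighted average of all 12 domain scores) are computed".

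**Status.** Section 8.2 says: "A detailed description of study procedures and study endpoints are provided in section of 5.0". Section 5.0 contains the list above.

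**Analysis.** Section 8.3 starts from the full Section 5.2 list ("The outcome measures for each subject (listed in Section 5.2) are recorded during 0th, 10th and 18th session of the training cycle") and continues: "Outcome measures are compared with in the subject and across the subject pools for statistical significant differences using Multiple ANOVAs". It then sets one level for everything: "All the statistics will be performed at 90% confidence level".

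The documents contain no exploratory label, testing order or multiplicity adjustment.

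**The concern.** Section 8.3 states a rule, and the rule reaches every listed measure. The nine measures outside the objectives get the same test at the same level as the primary outcome, and no text says what a significant result on one of them would mean.

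At a 10% error rate per test, a family of seven or more tests has a substantial chance of showing some arm difference in confidence, mood, participation or quality of life when none exists. As written, that result could be reported as a statistically significant finding of the trial. Settling the primary contrast or the TMS analysis would not change this, because these measures would still be tested at the full level.

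**Working it through.** **The plan's own figure.** The only error-rate figure is the 90% confidence level, so alpha is 0.10 per test. Sidedness is not stated; ANOVA F-tests are non-directional, so two-sided is taken. No family-wise figure is given, so there is none to reproduce.

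**Number of tests in the self-report set (Section 5.2, items 8-14).**
- Floor, one score per listed measure: 7.
- Upper count, if every described score is tested: mFES 1 + ABC 1 + SIS (8 + 1) + CPI 1 + pain 1 + PHQ-9 1 + SSQoL (12 + 1) = 27.
- Adding one score each for gait analysis and the FMA to the floor: 7 + 2 = 9. The number of gait parameters is left open in item 5, so 9 is a minimum.

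**Formulas.** With no true difference on any score, one between-arm test per score and one visit:
- Expected false positives = k × 0.10. For k = 7 this is 0.7; for k = 27 it is 2.7.
- Independent tests: P(at least one) = 1 − 0.9^k. For k = 7, 1 − 0.4783 = 0.522. For k = 9, 1 − 0.3874 = 0.613. For k = 27, 1 − 0.0581 = 0.942.
- Equal correlation ρ between test statistics: P = 1 − ∫ φ(u) [Φ((c − √ρ u)/√(1−ρ)) − Φ((−c − √ρ u)/√(1−ρ))]^k du, with c = 1.645, integrated numerically.

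| Tests | ρ = 0 | ρ = 0.3 | ρ = 0.5 | ρ = 0.7 |
|---|---|---|---|---|
| 7 (one per self-reported measure) | 52% | 47% | 40% | 32% |
| 9 (plus gait analysis, FMA) | 61% | 55% | 46% | 35% |
| 27 (all self-report scores) | 94% | 87% | 74% | 53% |

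Simulation with 100,000 draws per setting agrees within about one percentage point. The documents give no correlations; all values of ρ are assumptions.

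**Checks on the range.**
- The SSQoL summary is the mean of its domains. Building that into the simulation gives 94/86/73/52% for the 27 scores.
- Where the chance passes one half, at one visit: with 27 scores it is 53% at ρ = 0.7 and 47% at ρ = 0.75. With seven tests it is 50% at ρ = 0.2 and lower beyond.
- Two visits: the Section 5.3 table marks self-report at post-testing and follow-up. Testing both, with an assumed between-visit correlation of 0.7, gives 66/58/47% for seven measures and 97/89/72% for 27 scores at ρ = 0.3/0.5/0.7.
- Moving to alpha 0.05 without adjustment: 1 − 0.95^7 = 30% and 1 − 0.95^27 = 75% if independent. Changing the level alone does not solve it.

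The within-subject comparisons that Section 8.3 also plans are not counted.

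**The case against.** **The count of 27 is not documented as a count of tests.** Section 8.3 compares listed measures, and seven are self-reported. Only the SSQoL domain and summary scores are said to be computed, which is not the same as being tested, and no scoring rule is given for the SIS. This stands: seven is the floor, and 27 is an inference.

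**A reader might infer that a false finding is more likely than not.** The documents do not support that in general. At one visit it needs separate testing of the domains and a correlation no higher than about 0.7. With one score per measure it is about an even chance at best. The 94% figure assumes independence, which is implausible here: the SIS and SSQoL overlap in content, and the mFES and ABC both measure confidence in balance or stability.

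**A reader might infer that the plan has no hierarchy, so that a questionnaire score ranks with gait speed.** That is too strong. Sections 2.1 and 2.2 do rank primary and secondary objectives, and an unnamed measure can be read as ranking below both. What remains is that Section 8.3 does not carry the ranking into the testing rule.

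**A reader might take Section 2.3 as naming the questionnaires as endpoints.** Its clause "which will be the endpoints of the study" follows a list of visits and may mean time points. Section 8.2 is the better support.

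**Participants' knowledge of their arm.** The only blinding described is of the testing therapist, and one arm wears a device. This bears on bias in self-report. None of the figures above measures it.

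**Scope.** The named secondary measures are also tested unadjusted at 0.10, and the fix below does not address them. That is true, but it does not remove this point.

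**Conclusion.** The point holds in a limited form. Nine listed outcomes stand outside every objective, yet are significance-tested at the 90% level with nothing to mark them exploratory or control error. For the self-report set alone, the chance of at least one false arm difference at one visit runs from 32% (seven tests, correlation 0.7) to 94% (27 independent tests), about three to nine times the nominal 10%.

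This rests on no true difference on any score, two-sided tests, one between-arm test per score, and assumed equal correlations of 0 to 0.7. Within that range no count considered comes near 10%, so the conclusion does not depend on how the domains are treated. Only the size does. Because the remedy is wording alone, it is worth making.

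**What to change.** In Sections 2.3 and 8.3, state that:
- outcomes not named in Section 2.1 or 2.2 (Section 5.2, items 5 and 7-14) are exploratory;
- between-arm differences on them are reported with confidence intervals, for all scores and domains, at every visit where they are collected;
- they are not declared statistically significant and do not support a superiority claim.

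Before the list is final, reconcile two things:
- **Objective 2.2.3** ties stroke recovery to a step counter that is not in the Section 5.2 list, while the SIS and FMA, both described there as assessing recovery, are named in no objective. Labelling both exploratory without settling this would leave 2.2.3 with no listed measure.
- **Visit schedules.** Section 4.3 gives three data points and no follow-up. Section 5.2 gives four for all measures. The Section 5.3 table omits mid-testing for self-report.

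If the sponsor wants one confirmatory patient-reported result, name a single score in Section 2.2 (the SSQoL summary is one already defined) and test it only after a positive result on the primary contrast. That contrast needs a stated time point first.

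**Cost.** Text changes only, with no change to data collection or sample size. The downside is that a lone positive questionnaire score can no longer be reported as a confirmed study finding.

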5.3 Time and Events Table

	Consent, Baseline	Sessions 1-9	Mid Testing	Sessions 10-18	Post Testing	Follow up
Inclusion Exclusion	X					
Informed Consent	X					
History and PE	X					
SMA protocol or IPT protocol		X		X		
Clinical performance measures	X		X		X	X
Self-Reported Measures	X				X	X
TMS	X				X	X

5.4 Removal of Subjects from Study

- 5.4.1 Patient voluntarily withdraws from treatment
- 5.4.2 Patient withdraws consent (termination of treatment and follow-up);
- 5.4.3 Patient is unable to comply with protocol requirements
- 5.4.4 Patient demonstrates change in medical condition
- 5.4.5 Patient experiences adverse event that makes continuation in the protocol unsafe;
- 5.4.6 PI judges continuation in the study would not be appropriate;
- 5.4.7 Patient becomes pregnant

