4.2 Duration of Therapy

The Outpatient physical therapy sessions will last for a maximum of 18 visits per subject.

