4.4 Removal of Patients from Protocol Therapy

Patients may be removed from therapy if there is a change in medical status. The Principal Investigator may also decide if the patient is unable to continue for any extenuating circumstances to remove the subject from the study, and document the reason for study removal and the date the patient was removed in the Case Report Form.

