5.0 STUDY PROCEDURES

5.1 Screening/Baseline Procedures

Subjects will be randomized into 2 separate groups, either SMA or IPT. We will enroll 80 subjects, 40 in each group, planning for a 30% attrition rate. These subjects will be recruited when they are referred to RIC's stroke rehabilitation outpatient clinics at RIC's flagship at [name], or RIC Northshore in Northbrook IL or RIC Willowbrook in Willowbrook, IL. We will also recruit from local physicians or RIC's Clinical Neuroscience Research Registry for subjects who are potential candidates for outpatient physical therapy. They will be directed to a physical therapist who will inform them of the time commitment required and questioned regarding the inclusion/exclusion criteria. Once subjects have agreed to participate in the study, they will come to RIC and be consented at one of the clinics at the Rehabilitation Institute of Chicago. Study staff will explain the study, a written consent form will be signed by the subject and witnessed by study researchers, a copy will be given to the subject and a copy will be kept in the subject's folder in a secure, locked cabinet in the lab's locked office.

After consenting, subjects will undergo a physical evaluation and screening exam by a licensed PT. If they meet study criteria, they will be randomly placed into either the SMA group or the IPT group using a random number generator and they will be entered into the study. Once they are enrolled, baseline outcome measures will be assessed by a blinded research PT.

In addition, subjects will have a baseline measure of their cortical excitability through TMS. This will be conducted at University of Illinois, Department of Physical Therapy. TMS sessions will last approximately 2 hours.

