5.2 Procedures during Treatment

After the baseline testing is completed, subjects will begin 18 sessions of PT training in the outpatient clinic with a licensed RIC clinical PT. These sessions will last from 45 to 60 minutes. Their sessions will be recorded in RIC's electronic documentation system Cerner.

A blinded research physical therapist will test the outcome measure at baseline, Mid Testing after Session 9, at Post Testing after Session 18 and at 3 month follow up testing after Session 18.

IPT group	Baseline TMS	Baseline testing (blinded PT)	Sessions 1-9 3 x wk	Mid Testing (blinded PT)	Sessions 10-18 3 x wk	Post testing TMS	Post testing (blinded PT)	Follow up testing (blinded PT) 3 months post
SMA group	Baseline TMS	Baseline testing (blinded PT)	Sessions 1-9 3 x wk	Mid Testing (blinded PT)	Sessions 10-18 3 x wk	Post testing TMS	Post testing (blinded PT)	Follow up testing (blinded PT) 3 months post

The TMS protocol

We will test descending corticospinal drive to the rectus femoris, vastus lateralis, lateral hamstrings, tibialis anterior, and medial gastrocnemius muscles. These muscles have the biggest representation in the motor cortex and are most involved during the gait cycle.

Maximum Voluntary Isometric Contractions (MVIC): Before beginning the TMS protocol, an estimate of MVIC will be obtained for each muscle with the subject positioned in sitting on a chair, with the knee joint at 90 degrees of flexion and ankle in neutral position. Manual resistance will be provided by one of the investigators as the subject tries to extend or flex the knee, dorsiflex or plantarflex the ankle. Subjects will then be seated with the feet constrained by flexible 4.0 kg weights placed over the dorsum of each foot. The subject will be given real time feedback of muscle activity to match a target contraction corresponding to 10% MVIC for individual muscles during TMS measurements (details below).

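### The plan leaves unclear whether participants who stop treatment early are still tested, when they would be tested, and how they enter the gait-speed analysis

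*Combined protocol and SAP*

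**What the plan says.** **Removal.** Section 5.4 is headed as removal from the study. Its list includes "5.4.1 Patient voluntarily withdraws from treatment" and "5.4.4 Patient demonstrates change in medical condition", and also inability to comply and adverse events that make continuation unsafe. One item alone mentions the end of follow-up: "5.4.2 Patient withdraws consent (termination of treatment and follow-up".

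Section 4.4 concerns protocol therapy and begins "Patients may be removed from therapy if there is a change in medical status". It then passes to removal from the study, where the investigator is to "document the reason for study removal and the date the patient was removed in the Case Report Form". The TMS risk text in section 6.1.5 adds a further rule that withdraws a subject from the study for certain pain caused by the experiment.

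**Timing.** Section 5.2 places testing at baseline, then "Mid Testing after Session 9, at Post Testing after Session 18 and at 3 month follow up testing after Session 18". Section 2.3 uses the same session counts. Section 8.3 gives the 10th session for the mid test, then the 18th session and a 3-month visit.

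**Numbers and analysis.** Section 5.1 states "We will enroll 80 subjects, 40 in each group, planning for a 30% attrition rate". Section 8.3 specifies multiple ANOVAs at a 90% confidence level. It gives no analysis set, no handling of partial data and no sensitivity analysis. Section 2.1 names the 10 Meter Walk Test for the primary objective without a time point, and section 2.3 treats all four assessments as endpoints.

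**The concern.** Stopping treatment and ending outcome assessment are different events, and the removal rules do not keep them apart. A changed medical state is a ground for leaving therapy in section 4.4 and for leaving the study in section 5.4. A site that follows section 5.4 literally would stop testing someone who gives up the sessions but would gladly come back for a walk test. A site that wanted to test that person would find no date for doing so.

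These losses come after randomisation, which section 5.1 places even before the baseline measures. If they differ between arms in number, or in how they relate to recovery, a comparison of those still tested is biased in a direction that cannot be known beforehand. Unequal loss is plausible, because the skin and pressure problems from the exoskeleton in section 6.1.2 can arise in the SMA arm only. Measurements never taken cannot be recovered at the analysis stage.

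**Working it through.** **1. What is defined for whom**, reading sections 2.3, 5.2 and 8.3 together:
- Stops before the mid test: baseline only. No mid, post or 3-month test has a defined date.
- Stops after the mid test but before Session 18: baseline and mid test. The post and 3-month tests have no defined date.
- Completes 18 sessions: every test has a defined time.

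**2. How many people.** The enrolment of 80 cannot be reproduced, because no design effect, SD or power is given. Only the attrition step can be checked:
- 80 × 0.30 = 24 lost and 56 retained, or 28 per arm if loss is equal.
- 28 / (1 − 0.30) = 40 per arm, which agrees with section 5.1.

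**3. Bias from comparing only those retained.** Let p be the fraction of an arm's 40 that is lost, and g the mean gain of those retained minus that of those lost (S = SMA, I = IPT).

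Bias = pS × gS − pI × gI

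For g, I assume 0.06 to 0.14 m/s. Section 5.2 gives these values as small and substantial meaningful changes; they are not evidence about people who leave. Each case below loses 24 people in total, and the sign can go either way.
- 30%/30%, same gap in both arms: 0.30g − 0.30g = 0.
- 40%/20%, same gap in both arms: 0.20 × 0.06 = 0.012 to 0.20 × 0.14 = 0.028 m/s.
- 30%/30%, gap in one arm only: 0.30 × 0.06 = 0.018 to 0.30 × 0.14 = 0.042 m/s.

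**4. Effect on the test.** Take the 0.028 m/s case, with 24 and 32 people retained, no true effect and a two-sided 10% level (the documents do not state sidedness). The SE is SD × √(1/24 + 1/32). For an assumed SD of 0.25 down to 0.15 m/s, the error rate rises from 10% to about 13% to 18%.

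**5. What recovering early stoppers could achieve.** In the 30%/30% one-arm case, suppose a fraction r of those lost is tested after all and is typical of those lost.

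Remaining bias = 0.30g − g × 0.30r / (0.70 + 0.30r)

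For r = 0.50 (assumed) this is 0.124g, or 0.007 to 0.017 m/s, against 0.018 to 0.042 before. If those recovered did as well as those retained, the people still missing have a gap of g / (1 − r). The bias is then 0.30(1 − r) × g / (1 − r) = 0.30g, unchanged.

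**The case against.** The best reply is that only item 5.4.2 ends follow-up, so by contrast item 5.4.1 ends treatment alone. Other text leans the same way. Section 5.2 has the measures taken in both groups at all four points, the table in 5.3 puts no session condition on the post and follow-up columns, and 8.3 speaks of every subject. This stands in part. A reader might infer that section 5.4 settles that early stoppers are not tested, and the documents do not support that. But nothing tells staff to test them either. The heading of 5.4 covers all its items, and even on the generous reading the test date and the analysis rule are missing.

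Three other stronger readings also fail:
- From "The Outpatient physical therapy sessions will last for a maximum of 18 visits per subject" a reader might infer that the plan expects shorter courses. It may be only a cap, since the synopsis and section 5.2 both give 18 sessions.
- Section 7.1 gives three sessions a week for 6 to 8 weeks, from which a reader might infer a conflict with 18 sessions. It can equally mean 18 sessions in a window that allows for missed visits.
- A reader might take all 24 planned losses to be early stoppers who could be brought back. The 30% is general attrition. Some would be consent withdrawals, and some would be lost only at 3 months with a post test already done.

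Finally, the bias figures rest on assumed gaps and splits. That is true, and it limits the conclusion to possible bias.

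**Conclusion.** The concern holds as an ambiguity with a harmful consequence. The plan does not say whether people who stop treatment for reasons other than withdrawn consent are tested, gives no date for testing them, and gives no rule for analysing them. Followed as written, it can drop randomised participants from the primary comparison.

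Bias is possible, not shown. It is zero under like loss and about 0.01 to 0.04 m/s in the two unfavourable scenarios above. Those scenarios assume that the 24 planned losses occur and that gaps are 0.06 to 0.14 m/s. The documents give no split, timing or reasons for the attrition.

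A reader might infer that bias could by itself match the plan's small meaningful change of 0.06 m/s. For any split of 24 losses the ceiling is 0.60 × g. Reaching 0.06 therefore needs g of at least 0.06 / 0.60 = 0.10 m/s, together with all losses in one arm or opposite gaps in the two arms. Nothing in the documents points to either.

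The size also depends on the time point. People who stop after the mid test still contribute there, and no primary time point is named. The change is worth making because it is cheap and the missing measurements cannot be obtained later.

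**What to change.** 1. Leave the clinical criteria for stopping treatment unchanged. Reconcile sections 4.4, 5.4 and the TMS text in 6.1.5 so that stopping treatment does not by itself end outcome assessment.
2. State that, unless consent is withdrawn or a test is judged unsafe, early stoppers are invited to the remaining planned blinded tests at the calendar times these would have fallen, by the same rule in both arms. The 6 to 8 weeks in section 7.1 is the only calendar anchor for the treatment period, and should be read with sections 4.2 and 5.2 when the times are set. Record days from randomisation to each test for everyone.
3. In section 8.3, analyse all randomised participants in their assigned arm with a baseline-adjusted repeated-measures model that keeps partial data, and name the primary time point for the 10 Meter Walk Test contrast. State that this answers the question of effect regardless of stopping treatment. Someone with no post-baseline test adds little or nothing to such a model, so add a sensitivity analysis that makes missing gains worse by 0 to 0.14 m/s in each arm separately.
4. Section 4.4 already records the reason and date of study removal. Add the reason and date of stopping treatment and of each missed test, and report them by arm.

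The cost is wording plus modest effort to bring people back to visits already planned, with no added participants and no change to treatment. The trade-off is that stoppers are timed by calendar and completers by session count; the recorded days let this be checked. The statement in section 4.3 that there is no follow-up conflicts with the 3-month test elsewhere, and should be handled as a separate point.
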